7. TREATMENT AND/OR IMAGING PLAN

7.1 Investigational Agent Administration

Treatment will be on an outpatient basis. Reported AEs and potential risks for cobimetinib, hydroxychloroquine, and atezolizumab are described below (Section 8, Appendix 1). Appropriate dose modifications are described in Section 9. No investigational or commercial agents or therapies other than those described below may be administered to treat the patient's malignancy.

Patients will receive treatment as outlined in Table 4 below until unacceptable toxicity or loss of clinical benefit, as determined by the investigator after an integrated assessment of radiographic

Columbia University Irving Medical Center
Herbert Irving Comprehensive Cancer Center
AAAS4165_Version Date: 07/07/2021

and biochemical data, local biopsy results (if available), and clinical status (e.g., symptomatic deterioration such as pain secondary to disease).

Columbia University Irving Medical Center
Herbert Irving Comprehensive Cancer Center
AAAS4165_Version Date: 07/07/2021

Table 4. Treatment schedule

| Cycle | Cycle Length | Dose, Route and Regimen (drugs listed in order of administration) |
|--------------------|---------------------|--|
| Cycle 1 and beyond | 28 days | 
• Cobimetinib^a orally once daily (morning) on Days 1-21 of each 28-day• Hydroxychloroquine: 600mg orally twice daily on Days 1-28 of each 28-day cycle• Atezolizumab None or 840 mg IV on Days 1 and 15 of each cycle |

^aDose will be determined via dose levels

If one study drug is discontinued, the other study drug(s) can be continued if the patient is likely to derive clinical benefit, as determined by the investigator in consultation with the Principal Investigator.

7.1.1 Atezolizumab

Atezolizumab will be administered by IV infusion at a fixed dose of 840 mg on Days 1 and 15 of each 28-day cycle (Section 7.3).

Administration of atezolizumab will be performed in a monitored setting where there is immediate access to trained personnel and adequate equipment and medicine to manage potentially serious reactions.

Atezolizumab administration will be according to Table 5 below. Please note that Hydroxychloroquine and Cobimetinib could be administered in the morning, prior to Atezo.

Table 5. Atezolizumab administration

| First Infusion | Subsequent Infusions |
|---|---|
| 
• No premedication is permitted prior to the atezolizumab infusion.• Vital signs (pulse rate, respiratory rate, blood pressure, pulse oximetry, and temperature) should be recorded within 60 minutes prior to the infusion.• Atezolizumab should be infused over 60 (\pm 15) minutes.• If clinically indicated, vital signs should be recorded every 15 (\pm 5) minutes during the infusion and 30 (\pm 10) minutes after the infusion.• Patients should be informed about the possibility of delayed post-infusion symptoms and instructed to contact their study physician if they develop such symptoms. | 
• If the patient experienced an infusion-related reaction with any previous infusion, premedication with antihistamines, antipyretics, and/or analgesics may be administered for subsequent doses at the discretion of the investigator.• Vital signs should be recorded within 60 minutes prior to the infusion.• Atezolizumab should be infused over 30 (\pm 10) minutes if the previous infusion was tolerated without an infusion-related reaction, or 60 (\pm 15) minutes if the patient experienced an infusion-related reaction with the previous infusion.• If the patient experienced an infusion-related reaction with the previous infusion, or if clinically indicated, vital signs should be recorded during the infusion and at 30 (\pm 10) minutes after the infusion. |

Atezolizumab treatment may be interrupted for reasons other than toxicity (e.g., surgical procedures) with Principal Investigator approval. The Investigator and Principal Investigator will determine the acceptable length of treatment interruption.

7.1.1.1 Premedication

Premedication with antihistamines, antipyretics, and/or analgesics may be administered for the second and subsequent atezolizumab infusions only, at the discretion of the investigator. Hematopoietic growth factors are not to be administered prophylactically prior to the first dose of therapy. In general, investigators should manage a patient's care with supportive therapies as clinically indicated, per local standard practice. Patients who experience infusion-associated symptoms may be treated symptomatically with acetaminophen, ibuprofen, diphenhydramine, and/or H2-receptor antagonists (e.g., famotidine, cimetidine), or equivalent medications per local standard practice. Serious infusion-associated events manifested by dyspnea, hypotension, wheezing, bronchospasm, tachycardia, reduced oxygen saturation, or respiratory distress should be managed with supportive therapies, as clinically indicated (e.g., supplemental oxygen and β 2-adrenergic agonists; see Appendix 1).

Columbia University Irving Medical Center
Herbert Irving Comprehensive Cancer Center
AAAS4165_Version Date: 07/07/2021

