3.3.3 Contraindications

Hydroxychloroquine is contraindicated in patients with known hypersensitivity to 4-aminoquinoline compounds.

Adverse events noted from hydroxychloroquine include:

Ocular -

Irreversible retinal damage has been observed in some patients who have received hydroxychloroquine. Risk of this AE increases with dosage greater than 6.5mg/kg of actual body weight, use of durations greater than five years, subnormal glomerular filtration, use of some concomitant drug products, such as tamoxifen citrate, and concurrent macular disease.

Cardiotoxicity and QT Prolongation –

Columbia University Irving Medical Center
Herbert Irving Comprehensive Cancer Center
AAAS4165_Version Date: 07/07/2021

Postmarketing cases of lifethreatening and fatal cardiomyopathy have been reported. Patients may present with atrioventricular block, pulmonary hypertension, sick sinus syndrome, or cardiac complications. ECG findings may include atrioventricular right or left bundle branch block.

Worsening of psoriasis and porphyria –

Use of hydroxychloroquine in patients with this condition may precipitate a severe attack.

Proximal Myopathy and Neuropathy –

Progressive muscle weakness and proximal muscle group atrophy have been reported, including depressed tendon reflexes and abnormal nerve conduction.

Neuropsychiatric events, including suicidality –

Suicidal behavior has been rarely reported in patients treated with hydroxychloroquine.

Hypoglycemia –

Hydroxychloroquine has been reported to cause severe hypoglycemia, including loss of consciousness, which can be life threatening in patients who may or may not be on anti-diabetic therapy.

Other –

Hydroxychloroquine should be used in caution with patients who have compromised hepatic or renal function. Blood counts should be monitored to ensure no myelosuppression. Dermatitis has been reported with the use of hydroxychloroquine.

Drug Interactions –

Digoxin, insulin or other antidiabetics, drugs that prolong QT interval, antiepileptics, methotrexate, cyclosporine, praziquantel, antacids, cimetidine, and ampicillin have significant interactions with hydroxychloroquine.

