5. SUBJECT SELECTION AND WITHDRAWL

Each of the criteria in the following section must be met in order for a patient to be considered eligible for participation.

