23. Grade \geq 3 hemorrhage or bleeding event within 28 days prior to initiation of study treatment

24. Prior autologous stem cell, allogeneic stem cell, or solid organ transplantation

25. History of malignancy

Patient may not have a history of malignancy other than PDA within 2 years prior to screening, with the exception of those with a negligible risk of metastasis or death (e.g., 5-year overall survival of $> 90\%$), such as adequately treated carcinoma *in situ* of the cervix, non-melanoma skin carcinoma, localized prostate cancer, ductal carcinoma *in situ*, or Stage I uterine cancer.

26. Recent vaccination

Patients may not have been treated with a live, attenuated vaccine within 4 weeks prior to initiation of study treatment, or anticipate the need for such a vaccine during treatment with atezolizumab or within 5 months after the last dose of atezolizumab.

27. History of severe allergic anaphylactic reactions to chimeric or humanized antibodies or fusion proteins

28. Known allergy or hypersensitivity to 4-aminoquinoline compounds or any of the study drug excipients

29. Recent immunosuppressive treatment

Patients may not have been treated with systemic immunosuppressive medication (including, but not limited to, corticosteroids, cyclophosphamide, azathioprine, methotrexate, thalidomide, and anti-tumor necrosis factor alpha agents) within 2 weeks prior to initiation of study treatment, or

Columbia University Irving Medical Center
Herbert Irving Comprehensive Cancer Center
AAAS4165_Version Date: 07/07/2021

anticipate the need for systemic immunosuppressive medication during the course of the study, with the following exceptions:

- Patients who received mineralocorticoids (e.g., fludrocortisone), corticosteroids for chronic obstructive pulmonary disease or asthma, or low-dose corticosteroids for orthostatic hypotension or adrenal insufficiency are eligible for the study if receiving equivalent to < 10mg of prednisone daily.
- Patients who received a one-time pulse dose of systemic immunosuppressant medication are eligible for the study after approval from the Principal Investigator.

30. Inability to swallow medication or malabsorption condition that would alter the absorption of orally administered medications

31. History of retinal pathology

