38. History of connective tissue disorders (e.g., lupus, scleroderma, arteritis nodosa)

39. Subjects on greater than once daily dose of antacid therapy

40. Concomitant use of any of the following drugs:

- Digoxin
- Pharmacological agents known to prolong QT interval
- Mefloquine or other agents which may lower the convulsive threshold
- Antiepileptics
- Methotrexate
- Cyclosporine
- Ampicillin
- Cimetidine

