7.2.2 Medications Prohibited

- Live, attenuated vaccines (e.g., FluMist®) are prohibited within 4 weeks prior to initiation of study treatment, during treatment with atezolizumab, and for 5 months after the last dose of atezolizumab.
- Systemic immunostimulatory agents (including, but not limited to, interferons and interleukin 2) are prohibited within 12 weeks or five half-lives of the drug, whichever is longer, prior to initiation of study treatment and during study treatment because these agents could potentially increase the risk for autoimmune conditions when given in combination with atezolizumab.
- Systemic immunosuppressive medications (including, but not limited to, cyclophosphamide,

Columbia University Irving Medical Center
Herbert Irving Comprehensive Cancer Center
AAAS4165_Version Date: 07/07/2021

azathioprine, methotrexate, and thalidomide) are prohibited during study treatment because these agents could potentially alter the efficacy and safety of atezolizumab.

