10.1.6 Prior and Concomitant Therapy

Refer to Inclusion/Exclusion criteria (Sections 5.1 - 5.2).

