
Columbia University Irving Medical Center
Herbert Irving Comprehensive Cancer Center
AAAS4165_Version Date: 07/07/2021

| | |
|---------------------------|---|
| | 
if event resolves to Grade 1 or better within 12 weeks;
 
 • Resume Cobimetinib with dose reduced by 1 level if event resolves to Grade 1 or better within 28 days • If event does not resolve, permanently discontinue atezolizumab (if applicable) and cobimetinib and contact PI. |
| Diarrhea colitis, Grade 4 | 
 • Permanently discontinue atezolizumab (if applicable) and cobimetinib and contact PI; • Refer patient to GI specialist (confirmation and biopsy); • Discontinue medications that may exacerbate colitis while investigating etiology; • If Received Atezolizumab – 
 • Initiate treatment with 1-2 mg/kg/day oral prednisone or equivalent. Convert to 1-2 mg/kg/day oral prednisone or equivalent upon improvement; • If event does not improve within 48 hrs after starting corticosteroids, consider immunosuppressive agent; • If event resolves to Grade 1 or better, taper corticosteroids over ≥ 1 month. |

Table A1.3. Guidelines for managing dermatologic events in response to *atezolizumab, cobimetinib, and/or hydroxychloroquine*

| Event | Action |
|------------------|---|
| General guidance | 
 • Seek dermatologic evaluation for persistent and/or severe rash or pruritis • Consider biopsy unless contraindicated |
| Grade 1 or 2 | 
 • Continue atezolizumab (if applicable), cobimetinib, and hydroxychloroquine • Initiate supportive care. If event does not improve, consider treatment with higher potency topical steroids. • For Grade 2, consider referral to dermatologist • For acneiform rash: consider initiating treatment with topical corticosteroids and oral antibiotics, as clinically indicated. |

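### Section 7.1.1.1 offers cimetidine for infusion symptoms without caution, although exclusion 40 lists it and Section 3.3.3 flags its interaction with hydroxychloroquine

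*Combined protocol and SAP*

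**What the plan says.** The combined protocol and SAP names cimetidine three times.

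- **Section 7.1.1.1 (Premedication):** patients with infusion-associated symptoms "may be treated symptomatically with acetaminophen, ibuprofen, diphenhydramine, and/or H2-receptor antagonists (e.g., famotidine, cimetidine"), or with equivalent drugs under local practice. The section contains no caution about cimetidine.
- **Section 5.2, exclusion 40:** under the heading "Concomitant use of any of the following drugs", cimetidine is the last of 8 entries.
- **Section 3.3.3 (Contraindications):** "Digoxin, insulin or other antidiabetics, drugs that prolong QT interval, antiepileptics, methotrexate, cyclosporine, praziquantel, antacids, cimetidine, and ampicillin have significant interactions with hydroxychloroquine".

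Four other places bear on how these fit together. Section 10.1.6, on prior and concomitant therapy, consists only of a pointer: "Refer to Inclusion/Exclusion criteria (Sections 5.1 - 5.2"). Section 5 opens by presenting its criteria as conditions of entry: "Each of the criteria in the following section must be met in order for a patient to be considered eligible for participation". Section 7.2.2, the list of medications prohibited on study, does not include cimetidine. Section 7.2.1 gives a general instruction to check concomitant drugs against their prescribing information, and does not name cimetidine either.

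**The concern.** A site treating an infusion reaction will turn to Section 7.1.1.1, where a drug named as an example looks already cleared for use. Nothing there tells the reader that the same drug is listed in exclusion 40 or flagged in Section 3.3.3.

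At stake is a small, avoidable exposure to a drug that the protocol itself identifies as interacting with one of the study agents. The Cycle 1 infusions also fall inside the 28-day DLT window, and three early infusion days (Cycle 1 Days 1 and 15, Cycle 2 Day 1) are hydroxychloroquine PK sampling days under Table 9. Keeping a flagged drug away from those days makes the data easier to interpret. The documents give neither direction nor size for the interaction, so no effect on drug levels or toxicity is asserted.

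**Working it through.** The plan states no figure on this point to reproduce. The check sets the sections side by side and counts entries.

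**1. Is cimetidine singled out, or merely one of many flagged drugs?** The interaction sentence in Section 3.3.3 has 10 entries:

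| Entry in Section 3.3.3 | In exclusion 40? |
|---|---|
| Digoxin | Yes |
| Insulin or other antidiabetics | No |
| QT-prolonging drugs | Yes |
| Antiepileptics | Yes |
| Methotrexate | Yes |
| Cyclosporine | Yes |
| Praziquantel | No |
| Antacids | No (exclusion 39 excludes use more than once daily) |
| Cimetidine | Yes |
| Ampicillin | Yes |

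So 7 of 10 are in exclusion 40. Counting the partial limit on antacids in exclusion 39, 7 + 1 = 8 of 10 carry some restriction at entry. The eighth entry of exclusion 40 is mefloquine and other agents that lower the convulsive threshold (7 + 1 = 8 entries).

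**2. Does the interaction flag alone amount to a ban?** No. Insulin is in the same sentence, yet exclusion 11 admits patients with Type 1 diabetes on stable insulin, and Table A1.6 directs insulin for hyperglycemia. Cimetidine differs because it is both flagged and in exclusion 40.

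**3. Does exclusion 40 continue on study?** The text is ambiguous.
- For: Section 10.1.6 sends the reader on concomitant therapy to Sections 5.1 and 5.2.
- Against: Section 5 is framed as eligibility, and Section 7.2.2 omits cimetidine while listing other agents ("azathioprine, methotrexate, and thalidomide) are prohibited during study treatment").
- Against: entry exclusions are elsewhere set aside on study. Exclusion 29 bars patients who "anticipate the need for systemic immunosuppressive medication during the course of the study", with some exceptions, yet Table A1.2 in Appendix 1 directs steroids for colitis after atezolizumab: "Initiate treatment with 1-2 mg/kg/day oral prednisone or equivalent".

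No on-study ban can therefore be read into the plan with confidence, and none is needed for the point to hold.

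**4. Would cimetidine given under Section 7.1.1.1 coincide with hydroxychloroquine?** Yes, by schedule. Atezolizumab is given on Days 1 and 15 and hydroxychloroquine on Days 1–28, so 2 of 2 infusion days overlap. Section 7.1.1 allows the morning hydroxychloroquine dose before the infusion.

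**5. How often could it arise in phase 1?** Atezolizumab is given at dose levels 2 and 3 only: 2 of 3 levels, up to 2 infusions per 28-day cycle. The documents give no infusion-reaction rate, so no patient count follows.

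**6. Is an alternative already in the text?** Yes. Famotidine is named in the same example and appears in neither exclusion 40 nor the Section 3.3.3 sentence.

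**The case against.** The strongest reply is that no rule is broken. Exclusion 40 governs entry, Section 7.2.2 does not prohibit cimetidine, and Section 7.1.1.1 is permissive and concerns short-term symptom relief. The protocol often manages on-study reactions without repeating entry exclusions: besides steroids, Appendix 1 suggests oral antibiotics for acneiform rash despite exclusion 19, and an added immunosuppressive agent without repeating that methotrexate and cyclosporine are in exclusion 40. Section 7.2.1 tells investigators to check prescribing information and take questions to the Principal Investigator. No consequence is quantified, and a remedy that removes cimetidine goes further than adding a caution.

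Much of this stands. The point is not a breach, and its size is unknown. The same-day overlap also adds little by itself: Section 10.1.1 gives hydroxychloroquine half-lives of 537 hours in blood and 2,963 hours in plasma, so once treatment is established a patient carries the drug every day. That makes exposure continuous; it does not remove the overlap.

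Two parts do not dispose of the point. The Appendix 1 examples concern drug classes or a directed treatment for which the plan has evidently decided that need outweighs the entry restriction. Cimetidine is an individually named, interchangeable example, and nothing suggests such a decision was made. The general check in Section 7.2.1 is also less likely to be applied to a drug that the treatment section itself offers. As to the remedy, it does settle the matter for cimetidine in that one sentence, but at no loss, because famotidine remains.

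**Conclusion.** The concern holds, as a minor internal inconsistency. Section 7.1.1.1 should not offer, without caution, a drug that exclusion 40 bars at entry and Section 3.3.3 flags as interacting with hydroxychloroquine. In phase 1 its reach is limited to dose levels 2 and 3, and there to patients with infusion symptoms who are given cimetidine rather than an alternative.

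The conclusion rests on the text alone. It does not assume that exclusion 40 applies on study, and it assumes nothing about the direction or strength of the interaction. Design, sample size, error rates and analysis are untouched.

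**What to change.** In Section 7.1.1.1, delete cimetidine so that famotidine is the only H2-receptor antagonist named, and add the words *other than cimetidine* after the phrase that allows equivalent drugs under local practice.

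Do not copy the exclusion 40 list into Section 7.2.2. Whether its other entries, such as ampicillin, antiepileptics and QT-prolonging agents, should be prohibited on study is a separate clinical decision. Table A1.1 does not name cimetidine and needs no change.

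The cost is one example deleted and three words added in one sentence. The edit can go into the amendment already planned before phase 2 (Section 4.1.2), or into any earlier one.

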7.1.2 Cobimetinib

In this study, cobimetinib will be administered orally once daily (morning) on Days 1-21 of each 28-day cycle. Cobimetinib will be supplied as 20-mg, film-coated tablets packaged in blister packs (21 tablets per pack; 3 packs per box) for oral administration. Cobimetinib should be taken approximately the same time in the morning, and no later than 4 hours after the scheduled time. Cobimetinib may be taken with or without a meal. Cobimetinib should be swallowed whole with a glass of water and should not be chewed, cut, or crushed. If a dose of cobimetinib is missed (i.e., not taken within 12 hours after the scheduled dosing time), the patient should resume dosing with the next scheduled dose. Missed or vomited doses will not be made up. For information on the formulation and handling of cobimetinib, see the pharmacy manual and the Cobimetinib Investigator's Brochure.

7.1.3 Hydroxychloroquine

In this study, Hydroxychloroquine will be administered orally twice daily on Days 1-28 of each 28-day cycle with a meal or a glass of milk. Hydroxychloroquine should be swallowed whole with a glass of water (with meals) or milk and should not be chewed, cut, or crushed. If a dose of Hydroxychloroquine is missed (i.e., not taken within 6 hours after the scheduled dosing time), the patient should resume dosing with the next scheduled dose. Missed or vomited doses will not be made up.

Hydroxychloroquine treatment may be suspended for reasons other than toxicity with Principal Investigator approval.

7.1.4 Other Agent(s)

N/A

7.1.5 Other Modality(ies) or Procedures

N/A

7.2 General Concomitant Medication and Supportive Care Guidelines

The following are permitted therapies while receiving investigational agents.

- Oral contraceptives
- Hormone-replacement therapy
- Been stable on anticoagulation therapy (at a stable dose or low-molecular-weight heparin) that was initiated at least two months prior to initiation of study treatment.
- Inactivated influenza vaccinations
- Mineralocorticoids (e.g., fludrocortisone)
- Inhaled corticosteroids administered for chronic obstructive pulmonary disease or asthma
- Low-dose corticosteroids administered for orthostatic hypotension or adrenocortical

Columbia University Irving Medical Center
Herbert Irving Comprehensive Cancer Center
AAAS4165_Version Date: 07/07/2021

insufficiency amounting to less than 10mg of prednisone daily, and with the approval of the Principal Investigator.

- Hormonal therapy with gonadotropin-releasing hormone agonists or antagonists for prostate cancer
- Nerve blocks for pain control with adequate pain management

7.2.1 Medications to be given with precaution due to effects related to cytochrome P450 enzymes

Concomitant treatment is permitted if the medication is not expected to interfere with the evaluation of safety or efficacy of the study drug. During the study, if the use of any concomitant treatment becomes necessary (e.g., for treatment of an adverse event), the treatment must be recorded on the eCRF, including the reason for treatment, generic name of the drug, dosage, route, and start and stop dates of administration.

Concomitant use of strong and **moderate inhibitors of CYP3A** (e.g., clarithromycin, itraconazole, ketoconazole, posaconazole, telithromycin, and voriconazole; see Appendix 2) should be avoided during cobimetinib treatment because cobimetinib is a sensitive substrate of CYP3A, and exposures will be increased in the presence of these agents (approximately 7-fold increase in presence of itraconazole in healthy subjects). Consumption of grapefruit juice, a potent CYP3A4 enzyme inhibitor, is prohibited during the study and for 30 days after the last dose of study treatment.

Strong and **moderate CYP3A inducers** (e.g., rifampin, phenytoin, carbamazepine, and phenobarbital; see Appendix 2) should be avoided during cobimetinib treatment because they increase the metabolism of cobimetinib. Strong inducers of CYP3A4 should be avoided, or selection of an alternate concomitant medicinal product with no or minimal potential to induce CYP3A4 should be considered.

The above lists of cautionary medications are not necessarily comprehensive. The Investigator should consult the prescribing information when determining whether a concomitant medication can be safely administered with study treatment. In addition, the Investigator should contact the Principal Investigator if questions not listed above arise regarding medications.

